6.0 ENDPOINT ASSESSMENT

6.1 Primary Endpoint

The primary endpoint is the determination of the dose limiting toxicity and maximum tolerated dose (recommended Phase II dose) using a 3+ 3 design. It was determined by dose escalation schema.

6.2 Secondary Endpoints

This phase 1 study is not powered to detect statistically significant differences in efficacy.

However, data will be collected and described descriptively on the following endpoints:

- objective tumor response: objective response to therapy as determined by iRANO criteria (table 9)
- overall survival : time from study project injection to death
- progression-free survival : time from study project injection to first confirmed disease progression as determined by objective tumor response
- quality of life: summary score on patient self-report measure, Functional Assessment of Cancer Therapy- Brain component (as determined by patient self-report on FACT-Br v4, appendix C)

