4.9 Duration of Follow Up

Patients will have a follow-up visits days 1-3 while hospitalized, days 7, 14, and 28 after NSC-CRAd-S-pk7 administration and then at day 56, and every 8 weeks after until disease progression or patient withdrawal. They will be monitored for toxicities by physical exam and laboratory results through day 56. They will also undergo a brain MRI on day 28 and at day 56 to monitor for toxicity and disease progression, then every 8 weeks to monitor for disease progression. Survival status will be monitored until patient death or for up to 5 years.

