10.2 Sample Size and Accrual

This phase 1 study is not powered to detect statistically significant differences in efficacy. The primary endpoint of this Phase I dose-escalation study is the MTD of NSC-CRAd-S-pk7 when administered with standard radiation and chemotherapy in patients with malignant glioma. The 3+3 design has a 71% chance (49%, 17%) of dose escalating when the true toxicity rate for that dose is 20% (30%, 50%).

If all three dose levels are administered, the minimum number of patients enrolled will be 9 per arm and the maximum number of patients will be 18 per arm, for total accrual of 18-36 patients enrolled. Based upon the dose escalation schema described, groups of three to six patients will be entered at a dose level in each arm. Using this algorithm, the probabilities of dose escalation for various true DLT rates are given in Table 10. For example, if the true DLT is 50% at a dose level, there is a 17% chance that the dose would be escalated. The maximum tolerated dose determined in this study will be the recommended dose for a Phase II study. In the event the final pathology reading reveals anything other than a malignant glioma, such a patient will not be counted as one of the minimum number required without DLT for advancement to the next dose level but will be counted if a DLT is experienced.

Table 10– Probabilities of Dose Escalation	
20%	71%
30%	49%
40%	31%
50%	17%
60%	8%

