10.3.2 Description of Statistical Methods

10.3.2.1 General Approach

All study data will be presented in by-subject data listings. Statistical analysis will be descriptive only, with no hypothesis testing. All the endpoint data will be collected and described in summary tables for both two arms at each dose. In general, descriptive statistics (n, mean, standard deviation, median, minimum, and maximum) will be presented for continuous variables. Frequencies and percentages will be calculated for categorical and ordinal variables at each category. Statistical analyses will be performed using SAS9.4 (SAS Institute Inc., Cary, NC)

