10.3.2.3 Analysis of the Secondary Endpoint(S)

For objective tumor response, a summary table will be produced to present the number and proportion of responders in each arm, together with each of the response categories, namely CR, PR, MR, SD, P and PP.

The analysis of overall survival and progression-free survival are based on the survival function, estimated by the Kaplan-Meier method. Survival will be calculated from the day of study inclusion until progression and death, respectively, or will be censored at the date of last available follow-up information. The survival function will be summarized for 25th percentile, median, and 75th percentile, and the survival curves of the two arms will be presented.

Descriptive statistics will be used to describe the overall quality-of-life score on physical well-being, social/family well-being, emotional well-being, functional well-being and additional concerns, respectively.

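### PFS as defined has no death term: it is time to progression under another name, and a death without documented progression would be censored

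*Combined protocol and SAP*

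**What the plan says.** Section 6.2 lists two time-to-event endpoints. Overall survival (OS) is "overall survival : time from study project injection to death". PFS is "time from study project injection to first confirmed disease progression as determined by objective tumor response". Death appears only in the OS line.

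Section 10.3.2.3 gives the analysis: "The analysis of overall survival and progression-free survival are based on the survival function, estimated by the Kaplan-Meier method". Time then runs "until progression and death, respectively, or will be censored at the date of last available follow-up information". The curves of the two arms and the quartiles are to be shown, and the Study Summary adds medians with confidence limits for both endpoints.

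Section 4.9 shows that death dates will be available: "Survival status will be monitored until patient death or for up to 5 years". It schedules MRI at days 28 and 56 and then every 8 weeks. Table 4 in Section 5.0 adds an annual MRI for five years.

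Section 10.3 promises a formal SAP with further detail before database lock. Nothing in the present documents makes death a PFS event.

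**The concern.** PFS normally ends at the first of progression or death. Here a patient who dies before progression is documented has no PFS event, so the only rule left is censoring. Kaplan-Meier then treats that patient as someone who could still have progressed later at the same rate as the survivors. In malignant glioma that is doubtful, because death and progression are closely linked.

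Appendix A makes such cases possible. It defines progression by growth in tumor area on imaging and has no route based on clinical decline alone. A recent steroid reduction can also block the designation soon after radiation. A patient who deteriorates and dies without a qualifying scan would never be recorded as progressed.

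What is at stake is the meaning of the reported curve and median: a figure called PFS could not be set beside PFS that counts deaths. The censoring date adds a smaller problem, since it is not tied to a tumor assessment.

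**Working it through.** The documents state no PFS median, rate or event count, so there is no figure of the plan's to reproduce. The check has four steps.

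**1. Which events count.** Section 6.2 gives PFS progression only. In Section 10.3.2.3 the endpoints are named in the order OS, PFS, but the events in the order progression, death, followed by *respectively*. Read literally, PFS would end at death, which contradicts Section 6.2. Read in the evidently intended order, PFS ends at progression. Neither reading gives a combined event.

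**2. Direction.** The Kaplan-Meier estimate is the product, over event times, of (1 − 1/nᵢ), where nᵢ is the number at risk. If a death is treated as censored on the date of death (the last follow-up information for that patient), its factor (1 − 1/nᵢ) becomes 1 and the other risk sets do not change. The product can only stay the same or rise. This needs no assumption about hazards.

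**3. Size, under stated assumptions.** Let λp be the hazard of progression, λd the hazard of death without documented progression, both constant and independent, and d = λd/(λp + λd) the share of first events that are such deaths.

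- Median with deaths counted: ln 2/(λp + λd)
- Median with deaths censored: ln 2/λp
- Ratio: 1/(1 − d)

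The documents give neither d nor a median, so d is varied and a median of 7 months with deaths counted is assumed for illustration. The 12-month rate with deaths counted is 0.5^(12/7) = 30.5%. With deaths censored it is 0.5^((12/7)(1 − d)).

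| Assumed d | 1/(1 − d) | Median, deaths censored (months) | 12-month rate, deaths censored |
|---|---|---|---|
| 0% | 1.000 | 7.00 | 30.5% |
| 5% | 1.053 | 7.37 | 32.3% |
| 10% | 1.111 | 7.78 | 34.3% |
| 20% | 1.250 | 8.75 | 38.7% |
| 30% | 1.429 | 10.00 | 43.5% |

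Section 10.2 says "the minimum number of patients enrolled will be 9 per arm and the maximum number of patients will be 18 per arm" if all three dose levels are used. A simulation under the same assumptions (10,000 runs per setting, follow-up cut at 60 months) compared the two Kaplan-Meier medians at these sizes. The death-censored median was never earlier. It was later in these shares of runs:

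| Patients per arm | d = 5% | d = 10% | d = 20% | d = 30% |
|---|---|---|---|---|
| 9 | 18% | 34% | 59% | 76% |
| 18 | 38% | 61% | 86% | 96% |

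For scale, if every patient reaches a first event, two such deaths are 2/9 = 22% or 2/18 = 11% of an arm. The requirement in Section 4.2 for six patients at the MTD implies at least 3 + 3 + 6 = 12 when all three levels are used, where two deaths are 2/12 = 17%.

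**4. Censoring date.** For a patient alive without progression, last available follow-up may be later than the last scan. MRI continues every 8 weeks (Section 4.9), or every two to three months in the first year and then annually (Table 4). The excess is therefore the gap between scans, or longer for a patient who withdraws from treatment or misses scans but is still followed for survival.

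**The case against.** The strongest reply is that little depends on this. PFS is secondary, and Section 10.3.2.1 says "Statistical analysis will be descriptive only, with no hypothesis testing". OS is reported alongside it, all data are listed by subject and deaths are listed separately, so a reader could find any such death and recompute PFS. The wording of Section 10.3.2.3 is garbled rather than a deliberate rule to censor deaths, and the promised SAP could still settle it. *Confirmed* is undefined, and the progression row of Appendix A asks for no second scan, so fewer deaths may go unclassified than the word suggests.

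Most of this stands as a limit on importance. It does not remove the error. Section 6.2 already fixes the event without death, a later SAP is an opportunity rather than a cure, and listings do not correct a published curve.

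A reader might also infer that survival contact runs on for years after imaging stops, so that long unscanned periods count as progression-free for everyone. The schedules do not support that: progression-free patients stay on 8-weekly and then yearly MRI over the same five years. Only patients who withdraw or miss scans, and the gaps between scans, are affected.

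**Conclusion.** The point holds. As written, the endpoint is time to progression labelled PFS, and a patient who dies without documented progression is censored. The direction is certain: the curve and median are unchanged or higher.

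The size is conditional. With no such deaths the bias is zero. At assumed shares of 5, 10, 20 and 30% of first events the median is about 5, 11, 25 and 43% too long, given constant and independent hazards. It would go too far to say that PFS will be overstated by any of these amounts, because the documents give no rate of death before documented progression.

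It would also go too far to say that a Phase II trial would be planned on this PFS figure. What the documents carry forward is the dose. DLT assessment, escalation, the MTD and the sample size do not use PFS, so the impact is confined to a descriptive secondary endpoint. The wording should still be corrected.

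**What to change.** Change Sections 6.2 and 10.3.2.3 together:

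- Define PFS as time from injection to the first of progression (Appendix A) or death from any cause.
- Censor patients alive without progression at the date of their last evaluable MRI.
- State the event for OS and for PFS in separate sentences, so that nothing depends on *respectively*.
- Use one time origin. Section 6.2 counts from injection, while Section 10.3.2.3 says "Survival will be calculated from the day of study inclusion".
- Say what *confirmed* requires, given the pseudoprogression category in Appendix A.
- If time to progression is wanted, report it under that name as a supplement.

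The cost is wording only, since death dates and scans are already collected. The drawback is that reported PFS may be less favourable.

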6.3 Exploratory Endpoints

Correlation of cytokine profile and blood immune response with overall survival. Correlation of RCR testing with overall survival.

7.0 ADVERSE EVENTS

This study will be conducted in compliance with the Data Safety Monitoring Plan (DSMP) of the Robert H. Lurie Comprehensive Cancer Center of Northwestern University (please refer to Appendices for additional information).

We will institute a data safety monitoring board (DSMB) consisting of at least three experts in the field of neuro-oncology. The DSMB will review any complications arising from the proposed therapy prior to the enrollment of new patients. The DSMB will evaluate deaths that are considered by the PI to be possibly or probably related to the study agent in addition to the death considered related to the study agent.

Death of any patients within the first 56 days of treatment will be reviewed by DSMB within 7 days of the death. Until the review is completed, no new patients will be enrolled in the study. For a patient death that occurs after 56 days, the sponsor/investigator will determine if the death may be a result of the virotherapy. If the death is considered related to the therapy, enrollment will be placed on hold until the DSMB has discussed the case and the PI has discussed the death with the FDA.

In addition, the study will abide by all safety reporting regulations, as set forth in the Code of Federal Regulations.

7.1 Adverse Event Monitoring

Adverse event data collection and reporting, which are required as part of every clinical trial, are done to ensure the safety of subjects enrolled in the studies as well as those who will enroll in future studies using similar agents. Adverse events are reported in a routine manner at scheduled times during a trial (from screening through the Day 56 visit). In addition, certain adverse events must be reported in an expedited manner to allow for optimal monitoring and patient safety and care.

All patients experiencing an adverse event, regardless of its relationship to study drug, will be followed until:

- the adverse event resolves or the symptoms or signs that constitute the adverse event return to baseline;
- any abnormal laboratory values have returned to baseline;
- there is a satisfactory explanation other than the study drug for the changes observed; or
- death.

7.2 Definitions & Descriptions

7.2.1 Adverse Event

An adverse event (AE) is any untoward medical occurrence in a patient receiving study treatment and which does not necessarily have a causal relationship with this treatment.

An AE can therefore be any unfavorable and unintended sign (including an abnormal laboratory finding), symptom, or disease temporally associated with the use of an experimental intervention, whether or not related to the intervention.

Recording of AEs should be done in a concise manner using standard, acceptable medical terms. In general, AEs are not procedures or measurements, but should reflect the reason for the procedure or the diagnosis based on the abnormal measurement. Preexisting conditions that worsen in severity or frequency during the study should also be recorded (a preexisting condition that does not worsen is not an AE). Further, a procedure or surgery is not an AE; rather, the event leading to the procedure or surgery is considered an AE.

If a specific medical diagnosis has been made, that diagnosis or syndrome should be recorded as the AE whenever possible. However, a complete description of the signs, symptoms and investigations which led to the diagnosis should be provided. For example, if clinically significant elevations of liver function tests are known to be secondary to hepatitis, "hepatitis" and not "elevated liver function tests" should be recorded. If the cause is not known, the abnormal test or finding should be recorded as an AE, using appropriate medical terminology (e.g/ thrombocytopenia, peripheral edema, QT prolongation).

7.2.2 Severity of AEs

All non-hematologic adverse events will be graded according to the NCI Common Terminology Criteria for Adverse Events (CTCAE) version 4.03. The CTCAE v4 is available at <http://ctep.cancer.gov/reporting/ctc.html>

If no CTCAE grading is available, the severity of an AE is graded as follows:

- Mild (grade 1): the event causes discomfort without disruption of normal daily activities.
- Moderate (grade 2): the event causes discomfort that affects normal daily activities.
- Severe (grade 3): the event makes the patient unable to perform normal daily activities or significantly affects his/her clinical status.
- Life-threatening (grade 4): the patient was at risk of death at the time of the event.
- Fatal (grade 5): the event caused death.

7.2.3 Serious Adverse Events (SAEs)

All SAEs, regardless of attribution, occurring from time of signed informed consent, through 56 days after the last administration of study drug, must be reported upon discovery or occurrence.

An SAE is defined in regulatory terminology as any untoward medical occurrence that:

- **Results in death.**

If death results from (progression of) the disease, the disease should be reported as event (SAE) itself.

- **Is *life-threatening*.**
The patient was at risk of death at the time of the event; it does not refer to an event that hypothetically might have caused death if it were more severe.
- **Requires *in-patient hospitalization or prolongation of existing hospitalization for ≥ 24 hours.***
- Results in ***persistent or significant disability or incapacity*.**
- Is a ***congenital anomaly/birth defect*.**
- Is an ***important medical event*** not consistent with the risk information described in the general investigational plan or elsewhere in the current IND, and the event is not anticipated from the subject's disease history or status.
- **Any significant new neurological deficit in the post-operative period (within 7 days), will be considered an SAE.** For study patients with a history of seizures prior to entry, a single seizure will be considered an AE, but not an SAE. An increase in the seizure frequency or severity in such patients will be considered an SAE
- Secondary malignancy, or
- Any event in which the severity or specificity is
- Any event that does not meet the above criteria, but that in the judgment of the investigator jeopardizes the patient, may be considered for reporting as a serious adverse event. The event may require medical or surgical intervention to prevent one of the outcomes listed in the definition of "Serious Adverse Event." For example: allergic bronchospasm requiring intensive treatment in an emergency room or at home; convulsions that may not result in hospitalization; development of drug abuse or drug dependence.

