7.3.2 Determining if Expedited Reporting is Required

This includes all events that occur within 56 days of the last dose of protocol treatment. Any event that occurs more than 56 days after the last dose of treatment and is attributed (possibly, probably, or definitely) to the agent(s) must also be reported accordingly.

- 1) Identify the type of adverse event using the NCI CTCAE v 4.03.
- 2) Grade the adverse event using the NCI CTCAE v 4.03.
- 3) Determine whether the adverse event is related to the protocol therapy.
Attribution categories are as follows:
 - Definite: AE is clearly related to the study treatment.
 - Probable: AE is likely related to the study treatment.
 - Possible: AE may be related to the study treatment.
 - Unlikely: AE not likely to be related to the study treatment.
 - Unrelated: AE is clearly NOT related to the study treatment.
- 4) Determine the prior experience of the adverse event.
Expected events are those that have been previously identified as resulting from administration of the agent. An adverse event is considered unexpected, for expedited reporting purposes only, when either the type of event or the severity of the event is not listed in:
 - the current protocol
 - the drug package insert
 - the current Investigator's Brochure

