7.3.3 Expedited Reporting of SAEs/Other Events

7.3.3.1 Reporting to the Northwestern University QAM/DMC

All SAEs must be reported to the assigned QAM within 24 hours of becoming aware of the event. Completion of the NU CRO SAE Form, provided as a separate document, is required.

The completed form should assess whether or not the event qualifies as a UPIRSO. The report should also include:

- Protocol description and number(s)
- The patient's identification number
- A description of the event, severity, treatment, and outcome (if known)
- Supportive laboratory results and diagnostics
- The hospital discharge summary (if available/applicable)

All SAEs will be reported to, and reviewed by, the DMC at their next meeting.

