8.1.10 Side effects

Toxicities Associated with Adenoviral Injection

In previous trials of intratumoral adenoviral injection, toxicity was rare, and overall, the approach has been well tolerated. A summary of grade 3 and 4 toxicities seen in the previous trials is provided in **Table 8** below. In the Phase I study in recurrent brain

tumors, CNS toxicity (lethargy, confusion, grade 3 hyponatremia, fever, leukocytosis, intratumoral hemorrhage in 1, hydrocephalus in the other) was observed in 2/2 patients at 2×10^{12} vp dose level. In the lower dose levels, no DLTs were observed but transient and less severe events included seizure, small intratumoral hemorrhage, worsening of neurologic symptoms, mild hyponatremia. One patient at the highest dose level in the prostate dose escalation study experienced grade 4 transient thrombocytopenia which was considered a DLT and also transient grade 3 elevation in liver transaminases.

Table 8 – Summary of Grade 3 and 4 Toxicities In Trials With Adenovirus		
Patient Characteristics	Treatment Specifics	Toxicity
Recurrent malignant gliomas IND 6371 13 patients Trask et al, 2000	Dose escalation: 2×10^9 vp, (2 pts) 2×10^{10} vp, (2 pts) 2×10^{11} vp, (7 pts) 2×10^{12} vp, (2 pts) Delivery: Stereotactic injection Prodrug: GCV Concurrent tx: none	CNS toxicity in 2/2 patients at 2×10^{12} vp dose level Therapy tolerated by other 11 patients including 7/7 patients treated at 2×10^{11} vp
Recurrent ovarian cancer, stage IIIC IND 7311 10 patients Hasenburg et al, 2001	Dose escalation: 2×10^{10} vp, (2 pts) 2×10^{11} vp, (2 pts) 2×10^{12} vp, (2 pts) 2×10^{13} vp, (4 pts) Delivery: Intraperitoneal Prodrug: ACV or Valacyclovir Concurrent tx: Topotecan	No significant toxicity attributable to gene therapy.
Recurrent prostate cancer IND 6636 18 patients Herman et al, 1999	Dose escalation: 2×10^9 vp, (4 pts) 2×10^{10} vp, (5 pts) 2×10^{11} vp, (4 pts) 2×10^{12} vp, (5 pts) Delivery: Intraprostatic Prodrug: GCV Concurrent tx: none	One patient at 2×10^{12} vp dose level had transient grade 4 thrombocytopenia and grade 3 hepatotoxicity
Recurrent prostate cancer (radiation failures), multiple injections 27 patients (18 new patients plus 9 additional injections in patients from first study) Shalev et al, 2000; Miles et al, 2001	Dose: $2-6 \times 10^{11}$ vp Delivery: Intraprostatic Prodrug: GCV Concurrent tx: none	Grade 3 hypertension in one patient requiring anti-hypertensive therapy

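### Section 7.2.3 builds expectedness into the important-medical-event criterion, so expected events that meet no other SAE criterion move from mandatory to discretionary reporting

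*Combined protocol and SAP*

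**What the plan says.** Section 7.2.3 lists alternative criteria for an SAE. Most carry no test of expectedness. Hospitalization, for instance, is simply "in-patient hospitalization or prolongation of existing hospitalization for ≥ 24 hours", and the post-operative rule reads "Any significant new neurological deficit in the post-operative period (within 7 days), will be considered an SAE". The important-medical-event bullet is different. It applies only if the event is "not consistent with the risk information described in the general investigational plan or elsewhere in the current IND, and the event is not anticipated" in light of the patient's disease.

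The last bullet is a catch-all for SAE reporting: "Any event that does not meet the above criteria, but that in the judgment of the investigator jeopardizes the patient, may be considered for reporting". One of its examples is convulsions that do not lead to hospitalization. The same section says that a single seizure in a patient with a seizure history is an AE and not an SAE.

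Section 7.3.2 takes up expectedness as its fourth step, after grading and attribution: "An adverse event is considered unexpected, for expedited reporting purposes only". Section 7.3.3.1 makes SAE status alone the trigger for the 24-hour report to the QAM, and adds: "All SAEs will be reported to, and reviewed by, the DMC at their next meeting". Under Section 7.3.1, expected events are among the routine AEs, which go to the eCRF and are reviewed by the DMC on the schedule of the monitoring plan.

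**The concern.** Seriousness is normally a matter of outcome or medical importance, and expectedness is judged afterwards to set a reporting clock. Sections 7.3.2 and 7.3.3.3 follow that order. The latter sends SAEs that do not meet the expedited conditions to the annual FDA report, so it presupposes that expected SAEs exist. The important-medical-event bullet reverses the order for one class of event.

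The class matters because it includes known risks of the product. For the lower dose levels of the earlier adenoviral brain-tumor trial, Section 8.1.10 reports that "transient and less severe events included seizure, small intratumoral hemorrhage, worsening of neurologic symptoms, mild hyponatremia". If such an event is medically important but meets none of the other criteria, two investigators can class it differently and both comply with the protocol. At stake are the prompt QAM report, assured review at the next DMC meeting, and a consistent SAE listing under Section 10.3.3.

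**Working it through.** No sample-size or power arithmetic applies. The check is a reading of the criteria side by side.

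**Step 1: which criteria depend on expectedness (Section 7.2.3).**

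| Criterion | Expectedness test? | Mandatory? |
|---|---|---|
| Death, life threat, disability, congenital anomaly, secondary malignancy | No | Yes |
| Hospitalization or prolongation of at least 24 hours | No | Yes |
| Significant new neurological deficit within 7 days of surgery | No | Yes |
| More frequent or more severe seizures in a patient with prior seizures | No | Yes |
| Important medical event | Yes, two conditions | Yes, if both are met |
| Catch-all | No | No, discretionary |

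One further bullet, on severity or specificity, breaks off in the supplied text. No weight is placed on it.

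**Step 2: the logic of the bullet.** Its two conditions are joined by *and*. An event fails if it is consistent with the IND risk information, or if it is anticipated from the disease. Either is enough to remove it.

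**Step 3: two cases.**

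- *First seizure in a seizure-naive patient, not life-threatening, no admission, no disability.* The seizure rule covers only patients with prior seizures. The other mandatory criteria are not clearly met. Seizure appears in Section 8.1.10, and Section 7.2.3 itself foresees patients who had seizures before entry. The important-medical-event bullet therefore does not reach the event if it is regarded as expected or anticipated. Only the catch-all remains.
- *Non-disabling neurological worsening after day 7, managed without admission.* The new-deficit rule has lapsed, while SAE collection runs to day 56. Worsening is listed in Section 8.1.10, and Section 4.2.1 recognizes complications that fit the natural history of the tumor. Again only the catch-all remains.

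**Step 4: what follows from SAE status.**

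| Item | Depends on SAE status? | Section |
|---|---|---|
| 24-hour QAM report | Yes | 7.3.3.1 |
| Review at next DMC meeting | Yes | 7.3.3.1 |
| SAE listing | Yes | 10.3.3 |
| DLT and MTD | No: CTCAE grade and attribution | 4.2, 4.2.1 |
| Eligibility as an unanticipated problem | No: seriousness is not required | 7.2.4 |
| AE tables and all-AE listings | No | 10.3.3 |

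**Step 5: scale.** The documents give no rate for events of this kind. With 3 to 6 patients at a dose level in an arm, one event classed differently is 1/6 = 17% to 1/3 = 33% of that level. This is the weight of one event, not an estimate of how often it happens.

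**The case against.** The strongest reply is that the flaw is confined to one bullet among several. The criteria for the gravest outcomes are free of it, and two of the other criteria are aimed at the neurological risks of the procedure. The catch-all exists precisely for what the earlier bullets leave out, so its convulsions example does not contradict the important-medical-event bullet. This stands, and it sets the size of the point. It does not remove the point, because the catch-all permits reporting without requiring it.

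It can also be said that the limiting words in Section 7.3.2 govern only the definition given there, and that Section 7.2.4 uses expectedness too. That is fair: the mismatch is one of structure, not a literal prohibition. But Section 7.2.4 defines a different category, and nothing in the protocol explains why one seriousness criterion alone should carry the test.

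Other safeguards remain. DLT-period data are submitted weekly (Section 11.4). The DSMB reviews complications before new patients enroll (Section 7.0). The DMC safety analysis follows the first and second subjects by 14 days and precedes escalation (Section 4.2.1). These limit the harm, though none makes the classification consistent.

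A reader might infer that every event type in Section 8.1.10 necessarily fails the bullet. The documents do not support that. The test refers to the general investigational plan and the IND, which are not supplied. Section 8.1.10 summarizes earlier adenoviral trials, several with a prodrug, and a more severe event need not be consistent with what is described there.

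**Conclusion.** Wrong as written, and minor. Expected important medical events that meet no other criterion move from mandatory to discretionary SAE reporting. Their 24-hour QAM report, next-meeting DMC review and place in the SAE listing then vary with the investigator.

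A reader might go further and infer that the product's known risks drop out of the SAE count, or that such events can never become SAEs. Neither follows: most criteria have no expectedness test, and the catch-all admits the remainder. Nor does the bullet alter dose escalation, the MTD, eligibility as an unanticipated problem, or the AE tables, since none of these depends on SAE status.

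The conclusion assumes that at least some events of the kind in Step 3 would be judged consistent with the IND risk information or anticipated from malignant glioma. The text of Sections 7.2.3, 4.2.1 and 8.1.10 makes this likely, but the IND itself was not available. How often such events occur cannot be stated from the documents.

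**What to change.** In Section 7.2.3:

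- Delete both conditions from the important-medical-event bullet.
- Merge that bullet with the last one, so that an important medical event judged to jeopardize the patient, or to need intervention to prevent another listed outcome, must be reported as an SAE whether or not it is expected.
- Reconcile the convulsions example with the statement that a single seizure in a patient with prior seizures is an AE only. If reporting becomes mandatory while both stay as they are, they will collide. The protocol should say which governs.

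Leave expectedness to step 4 of Section 7.3.2.

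The cost is a wording amendment, a matching edit to the SAE form instructions, and a few more SAE forms. No additional expedited FDA reports should follow. The text of Section 7.3.3.3 reserves the 7- and 15-day clocks for unexpected, associated SAEs. The 7- and 15-day rows of Table 6 cover only fatal, life-threatening, hospitalizing or disabling events and congenital anomalies, which are SAEs already.
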